10.3 CLINICAL EVALUATION OF LIVER INJURY

10.3.1 Introduction

Alterations of liver laboratory parameters, as described in [Section 5.2.2.1](#) (adverse events of special interests), are to be further evaluated using the following procedures.

10.3.2 Procedures

Repeat the following lab tests: ALT, AST, and bilirubin (total and direct) – within 48 to 72 hours. If ALT and/or AST $\geq 3 \times$ ULN combined with an elevation of total bilirubin $\geq 2 \times$ ULN are confirmed, results of the laboratory parameters described below must be made available to the investigator and to Boehringer Ingelheim as soon as possible.

In addition,

- obtain a detailed history of current symptoms and concurrent diagnoses and medical history according to the “DILI checklist” provided in the ISF
- obtain history of concomitant drug use (including non-prescription medications, herbal and dietary supplement preparations), alcohol use, recreational drug use, and special diets according to the “DILI checklist” provided in the ISF;
- obtain a history of exposure to environmental chemical agents (consider home and work place exposure) according to the “DILI checklist” provided in the ISF;

and report these via the eCRF (except for the rollover part).

Clinical chemistry:

alkaline phosphatase, albumin, PT or INR, CK, CK-MB, coeruloplasmin, α -1 antitrypsin, transferrin, amylase, lipase, fasting glucose, cholesterol, triglycerides

Serology:

Hepatitis A (Anti-IgM, Anti-IgG), Hepatitis B (HBsAg, Anti-HBs, DNA), Hepatitis C (Anti-HCV, RNA if Anti-HCV positive), Hepatitis D (Anti-IgM, Anti-IgG), Hepatitis E (Anti-HEV, Anti-HEV IgM, RNA if Anti-HEV IgM positive), Anti-Smooth Muscle antibody (titer), Anti-nuclear antibody (titer), Anti-LKM (liver-kidney microsomes) antibody, Anti-mitochondrial antibody

<project dependent: Epstein Barr Virus (VCA IgG, VCA IgM), cytomegalovirus (IgG, IgM), herpes simplex virus (IgG, IgM), varicella (IgG, IgM), parvovirus (IgG, IgM), toxoplasmosis (IgG, IgM)>

Hormones, tumour marker:

TSH

Haematology:

Thrombocytes, eosinophils

Proprietary confidential information © 2024 Boehringer Ingelheim International GmbH or one or more of its affiliated companies

- Provide abdominal ultrasound to rule out biliary tract, pancreatic or intrahpatic pathology, e.g. bile duct stones or neoplasm.
- Initiate close observation of subjects by repeat testing of ALT, AST, and total bilirubin (with fractionation by total and direct) at least weekly until the laboratory ALT and/or AST abnormalities stabilise or return to normal, then according to the protocol. Depending on further laboratory changes, additional parameters identified e.g. by reflex testing will be followed up based on medical judgement and GCP.

11 DESCRIPTION OF GLOBAL AMENDMENT

11.1 GLOBAL AMENDMENT 1

Number of global amendment	1
Date of CTP revision	04 Jul 2019
BI Trial number	1280.15
BI Investigational Product	Xentuzumab (BI 836845)
Title of protocol	An open-label phase I dose escalation trial of weekly intravenous administrations of BI 836845 in Japanese patients with advanced solid tumours
To be implemented only after approval of the IRB	
To be implemented immediately in order to eliminate hazard - IRB to be notified of change with request for approval	
Can be implemented without IRB approval as changes involve logistical or administrative aspects only	
Section to be changed Description of change	Throughout the Clinical Trial Protocol Changes by amendment of Clinical Trial Protocol Update version number, revision date etc.
Rationale for change	
Section to be changed Description of change Rationale for change	Synopsis Section 1.2 – DRUG PROFILE Addition of ‘xentuzumab’ Decide the generic name of BI 836845
Section to be changed Description of change Rationale for change	Synopsis Section 3.1.1 – Administrative structure of the trial Section 8.1 – STUDY APPROVAL, PATIENT INFORMATION, AND INFORMED CONSENT Changes of organisation and role names Re-organisation of sponsor

Section to be changed	Synopsis – Methodology FLOW CHART FLOW CHART – ROLLOVER PART Section 3 – DESCRIPTION OF DESIGN AND TRIAL POPULATION Section 4 – TREATMENTS Section 5 – VARIABLES AND THEIR ASSESSMENT Section 6 – INVESTIGATIONAL PLAN Table 10.1: 3 – Blood sampling scheme for Cycle 4 onwards Appendix 10.3.2 – Procedures Addition of rollover part Add procedures regarding rollover part
Section to be changed	Section 1.4 – CLINICAL INFORMATION Section 9.2 – UNPUBLISHED REFERENCES Change of description regarding Investigator's Brochure and the reference Refer the latest version of Investigator's Brochure
Section to be changed	Section 3.1 – OVERALL TRIAL DESIGN AND PLAN Section 7.3.4 – Interim analyses Addition regarding clinical trial report and change of interim analysis plan Clarify the procedure
Section to be changed	Section 3.1.1 – Administrative structure of the trial Section 4.1.3.1 – Initial dose and dose levels to be evaluated Section 5.2.2.2 – Adverse event and serious adverse event reporting Section 5.2.5 – Electrocardiogram Section 5.3.4 - Pharmacogenomic evaluation Section 8.3 – RECORDS Optimisation of terminology Change systems using in this trial. Adopt adequate terminologies
Description of change Rationale for change	

11.2 GLOBAL AMENDMENT 2

Number of global amendment	2
Date of CTP revision	29 Apr 2022
BI Trial number	1280.15
BI Investigational Product	Xentuzumab (BI 836845)
Title of protocol	An open-label phase I dose escalation trial of weekly intravenous administrations of BI 836845 in Japanese patients with advanced solid tumours
To be implemented only after approval of the IRB	
To be implemented immediately in order to eliminate hazard - IRB to be notified of change with request for approval	
Can be implemented without IRB approval as changes involve logistical or administrative aspects only	
Section to be changed Description of change	Section 2.3 – BENEFIT–RISK ASSESSMENT Update of risk-benefit evaluation in consideration of topline results of 1280-0022 trial
Rationale for change	Clarify the reason for termination of BI 836845 clinical development and cessation of further BI 836845 manufacturing
Section to be changed Description of change	Section 3.3.4.3 – Discontinuation of the trial by the sponsor Update of information that significantly affect continuation of trial
Rationale for change	Clarify the sponsor's decision
Section to be changed Description of change	Section 5.2.9 – Pregnancy testing Modification of information on methods and duration of contraception
Rationale for change	Refer to the latest subject information for updated appropriate methods and duration of contraception

2 LIST OF ABBREVIATIONS

Term	Definition / description
AE	Adverse event
AESI	Adverse event of Special Interest
ATC	Anatomical, Therapeutic, Chemical
AUC	Area under the curve
BI	Boehringer Ingelheim
BMI	Body mass index
BSA	Body surface area
CR	Complete response
CRF	Care report form
CT	Concomitant therapies
CTCAE	Common Terminology Criteria for Adverse Events
CTP	Clinical Trial Protocol
CTR	Clinical Trial Report
DBL	Database Lock
DLT	Dose limiting toxicity
ECG	Electrocardiogram
ENR	Enrolled set
EOT	End of treatment
IGF	Insulin-like growth factor
iPDs	Important protocol deviations
LLT	Lowest Level Term
Max	Maximum
MedDRA	Medical Dictionary for Regulatory Activities
Min	Minimum
MQRMs	Medical Quality Review Meetings
MRI	Magnetic Resonance Imaging
MS	MTD set
MTD	Maximum tolerated dose
NE	Not evaluable

Proprietary confidential information © 2018 Boehringer Ingelheim International GmbH or one or more of its affiliated companies

P25	25 th percentile
P75	75 th percentile
PD	Progressive disease
PK	Pharmacokinetics
PKS	Pharmacokinetics Set
PPS	Per Protocol Set
PR	Partial response
PT	Preferred term
RECIST	Response Evaluation Criteria In Solid Tumours
REP	Residual effect period
RPM	Report planning meeting
SAE	Serious adverse event
SD	Stable disease
SOC	System organ class
SOP	Standard Operating Procedures
TCM	Trial clinical monitor
TS	Treated set
TSAP	Trial statistical analysis plan
WHO DD	World Health Organisation – Drug Dictionary

Proprietary confidential information © 2018 Boehringer Ingelheim International GmbH or one or more of its affiliated companies

3 INTRODUCTION

As per ICH E9, the purpose of this document is to provide a more technical and detailed elaboration of the principal features of the analysis described in the protocol, and to include detailed procedures for executing the statistical analysis of the primary and secondary variables and other data.

This TSAP assumes familiarity with the Clinical Trial Protocol (CTP), including Protocol Amendments. In particular, the TSAP is based on the planned analysis specification as written in CTP (see in section “Statistical Methods and Determination of Sample Size”). Therefore, TSAP readers may consult the CTP for more background information on the study, e.g., on study objectives, study design and population, treatments, definition of measurements and variables, planning of sample size, randomisation. This TSAP follows Boehringer Ingelheims (BI) internal reference [\(1\)](#).

In general, study or trial medication refers to Xentuzumab.

SAS Version 9.4 or later version will be used for all analyses unless otherwise specified.

Proprietary confidential information © 2018 Boehringer Ingelheim International GmbH or one or more of its affiliated companies

4 CHANGE IN THE PLANNED ANALYSIS OF THE STUDY

4.1 ADDITIONS/NEW ANALYSES

Dose proportionality analysis and attainment of steady state analysis for some PK parameters will be conducted.

4.2 CHANGES

As a change from planned pharmacokinetic analysis, the following PK parameters will not be calculated:

AUC_{0-∞}, t_{1/2}, MRT, CL, Vz, V_{ss}

Exploratory PK analyses during the dose escalation phase of study 1280.1 (with qw dosing) and 1280.2 (q3w dosing) have revealed that the qw dosing schedule does not allow to describe the elimination phase of Xentuzumab accurately. Therefore, all PK parameters related to the elimination phase will not be calculated in study 1280.15.

To align with BI standard definition, duration of disease control is defined as the time from first treatment administration until the earliest of disease progression or death, among patients with disease control.

A Clinical Trial Report (CTR) may be written before all patients have discontinued trial medication to document the results of the primary endpoint analysis. If written, subsequent data collected up to the point of trial completion will be reported in a revision to this CTR.

4.3 CLARIFICATIONS

The following points warrant further clarification:

- The terms “progression”, “progressive disease” (PD) and “disease progression” will be used interchangeably within this document.
- The terms “treatment cycle” or “treatment course” will be used interchangeably throughout this document.
- The terms “study medication” and “trial medication” will be used interchangeably throughout this document.

Proprietary confidential information © 2018 Boehringer Ingelheim International GmbH or one or more of its affiliated companies

5 ENDPOINTS

5.1 PRIMARY ENDPOINT

The primary endpoint is the maximum tolerated dose (MTD) of trial medication based on the occurrence of dose limiting toxicity (DLT) during the first treatment course. The planned treatment course consists of 21 days.

MTD:

MTD is defined as the highest dose level examined of trial medication, at which no more than 1 out of 6 patients experienced a DLT during the MTD evaluation period. The MTD evaluation period is defined as the time from the first administration of Xentuzumab up to start of cycle 2. That means that the exact duration of this period will be derived for each patient. If the patient does not start cycle 2, a fixed duration of 21 days will be used.

In case the MTD will not be reached until 1400 mg, it will be deemed as a sufficient tolerability in Japanese patients with advanced solid tumours at 1400 mg.

5.2 SECONDARY ENDPOINTS

5.2.1 Key secondary endpoints

Not applicable.

5.2.2 Other secondary endpoints

There are no secondary endpoints.

[figure not shown]
Proprietary confidential information © 2018 Boehringer Ingelheim International GmbH or one or more of its affiliated companies

Proprietary confidential information © 2018 Boehringer Ingelheim International GmbH or one or more of its affiliated companies

Proprietary confidential information © 2018 Boehringer Ingelheim International GmbH or one or more of its affiliated companies

Proprietary confidential information © 2018 Boehringer Ingelheim International GmbH or one or more of its affiliated companies

Proprietary confidential information © 2018 Boehringer Ingelheim International GmbH or one or more of its affiliated companies

Proprietary confidential information © 2018 Boehringer Ingelheim International GmbH or one or more of its affiliated companies

6 GENERAL ANALYSIS DEFINITIONS

6.1 TREATMENTS

Patients will be analysed according to the cohort initially assigned. All planned analyses will be presented by this cohort, unless specified otherwise. Handling of patients where cohort assignment has not been followed will be handled on a case-by-case basis, to be agreed at report planning meetings or DBL meeting (but prior to database lock).

For safety summaries data recorded during the Residual Effect Period (REP) will be considered as on-treatment. For this trial, the length of the REP is 42 days.

The actual study periods and treatment codes are defined in a document entitled “8-7-other-sdtm-trial-arms-trial-elements”, which can be found in Data Management and Statistics (DMS) folder, Section 8, within BIRDS.

6.2 IMPORTANT PROTOCOL DEVIATIONS

No per protocol set (PPS) analysis will be performed for this study, hence, no patient will be excluded from the analyses. However patients with potentially important protocol deviations (iPDs) will be documented. The following list in Table 6.2: 1 of potentially iPDs will be used; note that this is a working list and may not be finalised until the final Report Planning Meeting (RPM) prior to database lock for the primary analysis. Potentially important protocol deviations will be handled according to BI standards (9).

During the study conduct, protocol deviation should be monitored and guidance for improving / teaching the respective sites should be discussed during the study Medical Quality Review Meetings (MQRMs).

Table 6.2:1 Important protocol deviations

Category/ Code		Description	Requirements	Exclude d from
A [1]		Entrance criteria not met		
	A1	Diagnosis of trial disease questionable	Inclusion criteria IN1 not met	None
	A2	Prohibited baseline condition, diagnosis or treatment	Inclusion criteria IN3 not met or Exclusion criteria EX1, 3-12, EX14-15 or EX17-19	None
	A3	Laboratory result indicating inadequate organ function at screening	Exclusion criteria EX2	None

Table 6.2:1 (continued)

Important protocol deviations

Proprietary confidential information © 2018 Boehringer Ingelheim International GmbH or one or more of its affiliated companies

Category/ Code		Description	Requirements	Exclude d from
	A4	Adequate archival tumour tissue not available	Exclusion criteria EX13	None
B [1]		Legal Criteria		
	B1	Informed consent not available / not done	Informed consent date missing or Inclusion criteria IN4 not met	All
	B2	Informed consent too late	Informed consent date was after Screening Visit date	None
	B3	Age limit for patient inclusion not adhered to	Inclusion criteria IN2 are not met or, Calculate age given the date of birth and date of informed consent: patients must be \geq 20 years old	All
C [2]		Trial medication and randomisation		
	C1	Time window deviation for procedures performed at screening	Assessment at screening not within 28 days prior to first treatment	None
	C2	Trial medication not given according to protocol	Dose reduction scheme not followed description in section 4.1.3.6 in CTP.	None
	C3	Infusion time for the investigational treatment outside of CTP specific boundaries	Check medical review of administration data. Total infusion time (allowing for interruptions) $<$ 60 minutes See the section 4.3 in CTP.	None
	C4	Patient assignment not followed	Patients do not receive the initial treatment they were allocated to	None

Table 6.2:1 (continued)

Important protocol deviations

Proprietary confidential information © 2018 Boehringer Ingelheim International GmbH or one or more of its affiliated companies

Category/ Code		Description	Requirements	Exclude d from
D [2]		Concomitant medication		
	D1	Prohibited treatment during trial conduct phase	Indicated by medical review of concomitant therapy use during study treatment according to section 4.2.2.1 in CTP. Discuss the list which is given by TCM during MQRM.	None
E [2]		Missing Data		
	E1	Imaging assessments not done according to CTP instructions	Imaging assessment should be performed at Screening and several time points thereafter (see table 6.7.2: 1).	None
	E2	Pregnancy test not done according to CTP instructions	Exclusion criteria EX16 or Pregnancy test missing.	None
F [2]		Trial Specific protocol deviations		
	F1	Other protocol deviations affecting patient rights or safety	Manual PVs can be collectively captured	None

[1] iPD will be derived automatically

[2] iPD will be identified via individual review at MQRM/RPM/DBL.

6.3 PATIENTS SETS ANALYSED

The following analysis sets will be defined for this trial:

- Enrolled set (ENR)

This patient set includes all patients with informed consent given. The enrolled set will be used for patient disposition tables.

- Treated set (TS)

This patient set includes all patients who are documented to have received and taken at least one dose of study medication during the treatment cycles (from day 1).

The TS will be used for all planned safety and efficacy analyses.

- MTD Set (MS)

Proprietary confidential information © 2018 Boehringer Ingelheim International GmbH or one or more of its affiliated companies

The MTD set defines the set of patients that are fully evaluable for the MTD in the first treatment course. The MTD set will be used for some safety analyses, this is specified in the technical TSAP.

Patients in the TS who were replaced within the MTD period of the trial will be excluded from the determination of the MTD. Patients in the TS who entered in an expansion cohort will be also excluded from the determination of the MTD. Replacement of patients of the study is defined in Section 3.3.5 of the CTP. The final list of replaced patients is supplied by the Trial Clinical Monitor (TCM) no later than the last report planning meeting before the database lock for the safety analysis.

- Pharmacokinetic set (PKS)

This patient set includes all patients in the treated set who have at least one valid drug plasma concentration available. The decision whether a concentration is considered valid or not will in general be made at the RPM before Database Lock (DBL). The PKS will be used for the PK analyses of the trial.

No per protocol population will be used for analyses.

6.5 POOLING OF CENTRES

This section is not applicable because there are no inferential statistics, and therefore there is no statistical model in which centre/country can be included.

6.6 HANDLING OF MISSING DATA AND OUTLIERS

In general, missing data will not be imputed, unless required for the following analyses and definitions. Then the rules as described below apply.

Missing dates that affect the evaluation of endpoints specified in relevant sections of this TSAP will be imputed utilising a “worst case” approach, which will be applied on a case-by-case basis (depending on the affected endpoint) and agreed to by the trial team members at the final RPM before database lock at the latest. The agreements are implemented in the technical TSAP.

6.6.1 Adverse events

Missing or incomplete AE dates are imputed according to BI standards [\(2\)](#).

6.6.2 Laboratory values at baseline

For missing laboratory data at Visit 1 (before the very first administration of study medication) data from preceding visits will be used if not obtained longer than 2 days before the very first treatment with study medication.

Proprietary confidential information © 2018 Boehringer Ingelheim International GmbH or one or more of its affiliated companies

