- Grade 3: Severe or medically significant but not immediately life-threatening; hospitalisation or prolongation of hospitalisation indicated; disabling; limiting self care ADL
- Grade 4: Life-threatening consequences; urgent intervention indicated
- Grade 5: Death related to adverse event

Causal relationship of adverse event

Medical judgment should be used to determine the relationship, considering all relevant factors, including pattern of reaction, temporal relationship, de-challenge or re-challenge, and confounding factors such as concomitant medication, concomitant diseases, and relevant history. Assessment of causal relationship should be recorded in the eCRFs. The reason for the decision on causal relationship needs to be provided in the eCRFs.

Yes: There is a reasonable causal relationship between the investigational product administered and the adverse event.

No: There is no reasonable causal relationship between the investigational product administered and the adverse event.

Worsening of underlying disease or other pre-existing conditions

Worsening of the underlying disease or of other pre-existing conditions will be recorded as an adverse event or a SAE in the eCRF.

Changes in vital signs, electrocardiogram, physical examination, and laboratory test results

Changes in vital signs, ECG, physical examination and laboratory test results will be recorded as an adverse event or SAE in the eCRF if they are judged clinically relevant by the investigator.

Adverse events of special interests

DLTs and DLT-equivalent adverse events (see [Section 4.1.3.2](#) for definition), and DILI are defined as “adverse events of special interests”. Adverse events of special interests are to be reported in an expedited manner similar to SAE even if they do not meet any of the seriousness criteria (see [Section 5.2.2.2](#) for details).

If a DLT or a DLT-equivalent adverse event is observed, or the investigator determines any DILI is related to the study treatment, the administration of the investigational drug and/or application of concomitant therapy must be managed according to [Sections 4.1.3.5, 4.1.3.6](#), and [4.2](#).

The DILI is defined as followings:

- For patients with normal liver function (ALT, AST, and bilirubin within normal limits) at baseline:
An elevation of AST and/or ALT $\geq 3 \times$ ULN combined with an elevation of bilirubin $\geq 2 \times$ ULN measured in the same blood draw sample

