- For patients with impaired function tests (AST and/or ALT $>$ ULN) at baseline:
An elevation of transaminase \geq (baseline + 4 \times ULN) combined with an elevation of total bilirubin $\geq 2 \times$ ULN measured in the same blood draw sample

Patients showing these laboratory abnormalities need to be followed up according to [Appendix 10.3.2](#) of this CTP and the “DILI checklist” provided in the ISF. Patients with abnormal liver function tests must have their abnormalities and the etiology documented in detail as baseline conditions. Every effort should be made to explain possible deteriorations of baseline conditions.

Other significant adverse events

Other significant adverse events are defined any adverse event caused by discontinuation of study treatment and/or dose reduction.

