7.4 HANDLING OF MISSING DATA

No imputation will be performed on missing efficacy data.

Missing baseline laboratory values will be imputed by the respective values from the screening visit.

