6.6.3 PK parameters

6.7 BASELINE, TIME WINDOWS, AND CALCULATED VISITS

6.7.1 Baseline

The last measurement observed prior to start of trial medication will be assigned to baseline. Note that for some trial procedures (for example body weight, vital signs, laboratory tests) this may be the value measured on the same day trial medication was started. In these cases it will be assumed that the measurements were taken prior to the intake of any study medication. For tumour assessment, baseline evaluations must be based on Magnetic Resonance Imaging (MRI) or Computed Tomography scans performed no more than 28 days prior to start of trial medication.

Study days and visits will be labelled according to the flow chart of the CTP.

Unless otherwise specified, baseline is defined as the latest time-point before the very first administration of any study medication. If this criterion is not fulfilled then no baseline will be derived.

Laboratory values:

Baseline is defined as the latest time-point before the very first administration of any study medication. For laboratory values where not only the examination date but also time are recorded, examination time has to be taken into account when defining baseline. That is, a laboratory value on the same date as the first study drug administration is considered as baseline value if and only if the recording time was before or the same as the time of first study drug administration.

If any of these times are missing and the date of laboratory value is equal to the date of first study drug administration, then the laboratory assessment will be considered as according to protocol, i.e. as prior to first study medication.

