7.8.2.2 Laboratory values of special interest

Drug-induced liver injury (DILI)

Criteria for 'potential' DILI can be found in Section 5.2.2.1 of the CTP.

Patients fulfilling these criteria will be followed up according to the procedures described in Section 10.3 of the CTP.

Patients with missing laboratory values for liver enzymes will be excluded from these analyses but will be presented separately in a listing.

Tabulations of hepatic enzyme elevations and liver laboratory values (see Section 5.2.2.1 of the CTP), including flags of true DILI cases, are created in accordance with the Food and Drug Administration (FDA) DILI guidance ([12](#)).

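### For a laboratory result missing at Visit 1, SAP 6.6.2 gives no baseline when the last pre-dose value is more than 2 days old, whereas protocol 7.4 and SAP 6.7.1 use the screening value

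*SAP*

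**What the plan says.** Three places set the laboratory baseline when the Visit 1 result is absent.

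- Protocol 7.4: "Missing baseline laboratory values will be imputed by the respective values from the screening visit". The only age limit is the screening window, Day -28 to -1 (protocol 6.2.1).
- SAP 6.7.1 gives a general definition, "Unless otherwise specified, baseline is defined as the latest time-point before the very first administration of any study medication". It then repeats the rule in a separate paragraph for laboratory values, "baseline is defined as the latest time-point before the very first administration of any study medication", this time without the opening proviso. Neither has an age limit for laboratory values.
- SAP 6.6.2, headed as dealing with laboratory values at baseline, says that for missing Visit 1 laboratory data "data from preceding visits will be used if not obtained longer than 2 days before the very first treatment with study medication".

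SAP 6.6 introduces its own rules with "In general, missing data will not be imputed, unless required for the following analyses and definitions". Nothing visible ranks 6.6.2 against 6.7.1. The visible text of SAP 4.2 records other departures from the protocol, such as the definition of duration of disease control, but not this one.

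Protocol 5.2.4 and the flow chart footnote on laboratory tests let a result from the 2 days before Visit 1 of a cycle serve as that visit's result.

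**The concern.** Two programmers working correctly from these documents could derive different baselines for the same patient. One would carry the screening value forward. The other would leave baseline empty, discarding a value that the protocol both requires to be collected and names as the replacement.

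The direct cost falls on the laboratory displays. A patient without a baseline has no change from baseline, which protocol 7.3.3 plans for all laboratory tests. Under SAP 7.8.2.1 the patient goes into the category for a missing baseline CTCAE grade.

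A second effect is possible. SAP 7.8.2.2 takes its criteria for potential DILI from protocol 5.2.2.1, and these depend on baseline. One criterion is "For patients with normal liver function (ALT, AST, and bilirubin within normal limits) at baseline"; the other begins "For patients with impaired function tests (AST and/or ALT" and applies when either enzyme is above the upper limit of normal (ULN). With no baseline, neither can be assigned.

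**Working it through.** The plan states no figure on this point, so the check applies the rules side by side and then follows the result through.

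**Step 1: the rules.** Take a patient with no Visit 1 result and a single earlier one, from screening. With only one earlier value, the screening value and the latest pre-dose value are the same.

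| Day of last pre-dose result | Protocol 7.4 | SAP 6.7.1, laboratory paragraph | SAP 6.6.2 |
|---|---|---|---|
| -2 or -1 | baseline | baseline | baseline |
| -28 to -3 | baseline | baseline | none |

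The screening window has 28 days. Two of them (Day -2 and Day -1) satisfy SAP 6.6.2, so the rules differ on 28 - 2 = 26 days.

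**Step 2: what SAP 6.6.2 adds.** Where it does supply a value (Day -2 or -1), protocol 5.2.4 already lets that result stand for Visit 1. As a missing-data rule it therefore adds nothing for the routine panel. Its only distinct effect is to withhold the protocol 7.4 fallback.

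**Step 3: weight of one patient.** The trial enters at most 6 + 6 + 6 = 18 patients evaluable for the MTD, plus 6 in an expansion cohort, so 24. Escalation cohorts hold 3 to 6 evaluable patients. One lost baseline is thus 1/6 to 1/3 of such a cohort.

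**Step 4: the DILI criteria, conditionally.** Suppose SAP 6.6.2 overrides 6.7.1. Protocol 5.2.2.1 sets the AST/ALT threshold, in multiples of ULN, at 3 if liver tests were normal at baseline and at baseline + 4 if AST or ALT was raised. Both also need bilirubin of at least 2. Protocol 3.3.3 admits AST/ALT up to 2.5, or 5 with liver metastases. Thresholds for raised baselines therefore run from just above 1 + 4 = 5 to 2.5 + 4 = 6.5, or to 5 + 4 = 9 with liver metastases.

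The values below are assumed for illustration: Visit 1 missing, screening 10 days before dosing, on-treatment bilirubin 2 x ULN, and other liver tests normal at screening.

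| Screening ALT (x ULN) | Threshold | On-treatment ALT (x ULN) | Protocol 7.4 and SAP 6.7.1 | SAP 6.6.2 |
|---|---|---|---|---|
| 0.8 | 3.0 | 3.5 | met | not assignable |
| 1.5 | 1.5 + 4 = 5.5 | 3.5 | not met | not assignable |
| 1.5 | 5.5 | 6.0 | met | not assignable |
| 2.5 | 2.5 + 4 = 6.5 | 6.0 | not met | not assignable |
| 5.0 | 5.0 + 4 = 9.0 | 9.0 | met | not assignable |

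With the screening result moved to 2 days before dosing, all three rules give the same answer in every row.

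**The case against.** The strongest reply is that the sections can be read together. SAP 6.6.2 speaks of data missing at Visit 1, which is a visit slot, and its 2-day limit matches the scheduling allowance in protocol 5.2.4. It says what will be used and does not expressly bar an older value from being baseline. Baseline is then left to SAP 6.7.1, and no patient loses one. This reading is possible but strained. The section heading refers to values at baseline, and on this reading the rule only repeats what the protocol already allows.

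A second reply is that the proviso in SAP 6.7.1 makes 6.6.2 the intended exception. The laboratory paragraph does not carry that proviso. Even if it did, the departure from protocol 7.4 would remain undeclared in the visible text.

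The objections to scale largely stand. Cycle 1 Day 1 laboratory tests are scheduled, a 2-day-old result may replace them, and the trial has one site. All analyses are descriptive.

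A reader might go further and infer that a DILI case would vanish from the report. The documents do not support that. It would need a missed Visit 1 panel, no result in the previous 2 days, SAP 6.6.2 overriding 6.7.1, later concurrent rises in enzymes and bilirubin, and an absent baseline that blocks tabulation. On the last condition SAP 7.8.2.2 says only "Patients with missing laboratory values for liver enzymes will be excluded from these analyses but will be presented separately in a listing", without stating whether a missing baseline counts. It refers the tabulations and the flags of true cases to an external guidance, and SAP 7.8.2.1 relies on a sponsor standard for laboratory data; neither is part of these documents. If the patient were excluded, the listing would show the case. If the investigator reported DILI, it would be in the AESI table.

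**Conclusion.** The inconsistency is in the text and worth removing, but its reach is small. On the natural reading of SAP 6.6.2, a patient with no Visit 1 result and a last pre-dose result on Day -28 to -3 has no laboratory baseline. Protocol 7.4 and the laboratory paragraph of SAP 6.7.1 both supply one. The firm consequence is a lost change from baseline and display in the missing-baseline-grade category for that patient. The effect on the potential-DILI criteria is a possibility only.

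The 26 of 28 days describe where the rules differ, not how often a patient falls there. The documents give no rate of missing Visit 1 results, and the case is probably rare. The MTD does not depend on this rule.

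The conclusion assumes that SAP 6.6.2 is meant to set the baseline, as its heading indicates, and that no document outside the two reviewed already settles the order of precedence.

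**What to change.** Replace the rule in SAP 6.6.2 with: *For laboratory data missing at Visit 1, the latest value before first administration, including the screening value, is used as baseline (CTP 7.4, TSAP 6.7.1); baselines older than 2 days are flagged in the listing.*

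This aligns all three places. Every patient with a screening result then has a baseline, so the DILI criteria cannot become unassignable through the 2-day rule. The cost is one sentence and one flag variable, with no new data. The downside is that a baseline may be up to 28 days old, which the flag makes visible.

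Keeping the 2-day limit and only declaring it in SAP 4.2 would document the departure but still discard the screening value. With the replacement sentence it is not needed.
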